# Statistical Analysis Plan

Name of the project:	International name: PIMPmyHospital (local name: PIMPmyHUG)
Name of the institution:	Geneva Children's Hospital, Geneva University Hospitals
Name of the PI:	[name]
Affiliation	Children's Hospital, Geneva University Hospitals, [name], contact: [contact]
National Clinical Trial Identifier Number	NCT05203146
Registered on	Jan 21, 2022
Funding	None
Sponsor	None
Version number	v.1.0, Jul 15, 2021
Statistical analyses	
For the primary outcome, we will assess the time taken in minutes for each allocation group to consider new laboratory results, whether accessed through the mobile app or the institutional Electronic Health Record (EHR). Normality analysis of continuous variables will be performed using the Shapiro–Wilks test. Given the anticipated non-normal distribution of data, the Mann–Whitney test will be employed for comparing independent groups. No paired data will be compared. Kaplan–Meier curves will be estimated, and bivariate survival analysis will use the log-rank (Mantel–Cox) test.
 
For the secondary outcome, we will assess the time taken in minutes from the participant's notification, either through the mobile app (intervention) or a statement from a study investigator (conventional method), indicating the need for assistance with a technical procedure, to the participant reaching the designated nurse. Similar analyses will be conducted for the secondary outcome.
 
All statistical tests will be two-tailed with a significance level of 5%. Data analysis will be carried out using Prism latest software version (GraphPad software, LLC., San Diego, CA, USA) for MacOS.

Interim analysis	We will not perform interim analyses as our trial has a short duration and no potential serious outcomes.
Handling of missing data	In the case of missing data, a complete case analysis will be conducted. No multiple imputations are planned.
Statistical tests	All statistical tests will be two-sided with a type I error risk of 5%. Data analysis will be carried out using GraphPad Prism latest software version for MacOS (GraphPad software, San Diego, CA, USA) for graph figures, descriptive statistics, and statistical tests.

Date and signature:

14 July 2021

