# Study Protocol

Name of the project:	International name: PIMPmyHospital (local name: PIMPmyHUG)
Name of the institution:	Geneva Children's Hospital, Geneva University Hospitals
Name of the PI:	[name]
Affiliation	Children's Hospital, Geneva University Hospitals, [name], contact: [contact]
National Clinical Trial Identifier Number	NCT05203146
Registered on	Jan 21, 2022
Funding	None
Sponsor	None
Version number	v.1.0, Jul 15, 2021
Objective(s)/Aim:	To assess the impact of a newly developed mobile application (PIMPmyHospital) on pediatric emergency physicians and nurses to improve remote collaborative and synchronous communication in a pediatric emergency department (via a chat messaging system) and to reduce the time spent walking/traveling in between destinations (emergency rooms, etc.) when caring for patients, when compared to current methods not using the mobile app. This app aims to provide relevant information in real-time about the patients they care for, as well as a secure chat and messaging platform to virtually connect physicians and nurses caring for the same patients.
Outcome/Endpoints	
Primary outcome  The time taken (in minutes, within a upper time limit set at 120 minutes) for each allocation group to consider new laboratory results, whether accessed through the mobile app or the institutional Electronic Health Record (EHR) patient data system, from the point of availability to participant review on the designated medium (mobile app or EHR).
 
Secondary outcomes  The time elapsed (in minutes, within a upper time limit set at 120 minutes) from the notification received by the participant through the mobile app or a statement from a study investigator (conventional method), indicating that a nurse needed assistance for a technical procedure, up to the moment when the participant reached the designated nurse.

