Project design and procedures	
This will be a single-center, non-blind, two-arm, randomized, controlled pilot trial. This study aims to assess two methods for processing laboratory results (specifically, the post-analytical phase) and facilitating collaborative actions in standardized, semi-simulated scenarios mimicking everyday situations within a Pediatric Emergency Department (PED). Participants will be randomly allocated to perform these actions either utilizing the dedicated mobile app PIMPmyHospital (intervention group) or employing conventional methods (i.e., the EHR, control group). The primary hypotheses posited that the use of the mobile app would result in a reduction in both the time taken to access laboratory results and the time required for remote communication with colleagues.
 
The trial will take place in a real-world environment at the Pediatric Emergency Department (PED) of the Geneva Children's Hospital, Switzerland, during caregivers' shifts, but no patients will be enrolled, nor

[figure not shown]
	
their medical data collected. The recordings will not be used for any purpose other than this project.
 
The trial will be registered on Clinicaltrials.gov.

Project population, inclusion and exclusion criteria	
A convenience sample of 10 caregivers. Eligible participants will be postgraduate residents pursuing a <6-year residency in pediatrics and registered nurses from the PED of the Geneva Children's Hospital (aged > 18 years). They must have previously completed a standardized 5-minute introductory course on app usage provided by the study investigators on the day of participation. Exclusion criteria encompass participants who have not completed the introductory course. Recruitment of participants adheres to Cohen's calculation, with an anticipated effect size of 2.0, a type I error of 0.05, and a power of 80%.

Recruitment, screening and informed consent procedure	
Participants will be recruited from the PED of the Geneva Children's Hospital. On the day of participation, in the presence of the study investigators, participants will provide informed consent, provided they had ample time for consideration and opportunity to ask questions. No financial compensation will be offered to participants.

Involvement of samples or health related data	
No patients will be enrolled in this trial. Hence, no patient's samples or data will be collected.

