Randomization and Blinding	
Participants will be randomized using a single, constant 1:1 allocation ratio determined through web-based software www.sealedenvelope.com. Allocation concealment will be maintained with the use of the allocation software, and it will not be released until participants initiate the scenario. To minimize preparation bias, participants will be kept unaware of the scenario during recruitment. Following randomization at the scenario's commencement, they will be unblinded to their assigned study arm. The study investigators involved in the scenario, assuming the role of a fellow nurse to be located by participants, will be revealed to participants before the scenario begins. All investigators will remain uninformed about the outcomes until all data are unsealed for analysis at the conclusion of the trial.

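### Two tests are planned on the one primary outcome, with neither the deciding test nor the p-value method named; at 10 participants this leaves both the 5% level and the 80% power unsecured

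*SAP*

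**What the plan says.** The SAP, under Statistical analyses, first expects non-normal data and says the Mann–Whitney "test will be employed for comparing independent groups". It then adds, for the same primary outcome, that Kaplan–Meier "curves will be estimated, and bivariate survival analysis will use the log-rank" (Mantel–Cox) test. The secondary outcome is to be analysed in a similar way. Under Statistical tests: "All statistical tests will be two-sided with a type I error risk of 5" per cent. The software is named, but no option for exact, permutation or large-sample p-values is given.

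The Protocol's Outcome/Endpoints section measures the time "within a upper time limit set at 120 minutes". Neither document says how a participant who has not finished by then is analysed. The SAP's only related rule, under Handling of missing data, is "In the case of missing data, a complete case analysis will be conducted".

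The sample is "A convenience sample of 10 caregivers" (Protocol, Project population), planned "with an anticipated effect size of 2.0, a type I error of 0.05, and a power of 80" per cent. Under Randomization and Blinding, "Participants will be randomized using a single, constant 1:1 allocation ratio".

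**The concern.** Two tests on one outcome can disagree, and the plan gives no order of precedence. If one is significant and the other is not, a report on either would comply with the SAP.

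The second gap is the p-value method. With about five people per arm there are only 252 possible allocations, so each test's attainable levels are coarse, and a large-sample reference distribution can miss the nominal 5% on either side. A plan that promises 5% needs a method that delivers it.

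At stake is whether a significant result on the primary outcome carries the stated false-positive risk, and whether the study has the power it states under the test it would actually use.

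**Working it through.** **Inputs.** N = 10, d = 2.0, alpha 0.05, power 80% (Protocol, Project population); 1:1 allocation (Randomization and Blinding), taken as 5 v 5; two-sided 5% (SAP, Statistical tests); limit of 120 minutes (Outcome/Endpoints). The number reaching the limit is not given, so 0 to 8 of 10 was examined. Distinct times below the limit, and the chi-square or normal reference, are assumptions.

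**The plan's own figure.** For a two-sided two-sample t-test with 5 per arm, the noncentrality is 2 × √(5/2) = 3.16, with 8 df and critical value 2.306. Power is 79.05%. The stated N = 10 for 80% is therefore reproduced, but for a t-test, which the SAP does not plan.

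**Level of each test.** All C(10,5) = 252 allocations were enumerated under no difference. The log-rank is (O − E)²/V with hypergeometric V, referred to chi-square on 1 df (3.841). Participants at the limit are censored for the log-rank and take the tied worst rank for Mann–Whitney.

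| At limit | Chi-square log-rank | Exact Mann–Whitney | Permutation log-rank |
|---|---|---|---|
| 0, 1 or 2 | 18/252 = 7.1% | 8/252 = 3.2% | 12/252 = 4.8% |
| 3 | 18/252 = 7.1% | 12/252 = 4.8% | 12/252 = 4.8% |
| 4 | 12/252 = 4.8% | 8/252 = 3.2% | 12/252 = 4.8% |
| 5 or 6 | 12/252 = 4.8% | 12/252 = 4.8% | 12/252 = 4.8% |
| 7 | 42/252 = 16.7% | 0 | 0 |
| 8 | 0 | 0 | 0 |

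In every row, claiming success on either the chi-square log-rank or the exact Mann–Whitney has the same level as the chi-square log-rank alone.

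*Hand check of the row with seven at the limit.* If all three events fall in one arm, O = 3, E = 5/10 + 4/9 + 3/8 = 1.319 and V = 25/100 + 20/81 + 15/64 = 0.731. The statistic is 1.681²/0.731 = 3.86, above 3.841. This happens in 2 × C(7,2) = 42 allocations.

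**Mann–Whitney by normal approximation, no ties.** The mean of U is 12.5 and its variance is 5 × 5 × 11/12 = 22.92, so the SD is 4.79. At U = 3, z = 9.5/4.79 = 1.98, above 1.96, so U ≤ 3 or U ≥ 22 rejects: 2 × (1 + 1 + 2 + 3) = 14, and 14/252 = 5.6%. The exact test stops at U ≤ 2 or U ≥ 23: 2 × (1 + 1 + 2) = 8.

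**Disagreement.** With no ties and nobody at the limit, 10 of 252 allocations (4.0%) are significant by chi-square log-rank but not by exact Mann–Whitney, and none the other way. Four of those 10 are also significant by permutation log-rank.

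**Ties, nobody at the limit.** Over the 89 patterns with no tie larger than a pair, the chi-square log-rank rejects in 12 to 24 of 252 and exceeds 5% in 87. Over all 511 tie patterns it rejects in 0 to 42 of 252 and exceeds 5% in 322. Exact Mann–Whitney never rejects more than 12 of 252.

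**Uneven arms, none to two at the limit.** Chi-square log-rank: 16/210 = 7.6% at 4 v 6 and 10/126 = 7.9% at 4 v 5.

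**Power at 5 v 5, normal data, by simulation.** At d = 2, exact Mann–Whitney has 0.676 and permutation log-rank 0.728 to 0.745, depending on the statistic. The chi-square log-rank has 0.784, at a level above 5%. Exact Mann–Whitney reaches 0.796 at d = 2.3.

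**The case against.** The SAP does imply an order. Mann–Whitney comes first and is the test named for comparing the groups; the log-rank is attached to the survival curves. On that reading, with an exact p-value, the level is at most 4.8% and only a label is missing. This largely stands. A reader might infer that the text supports a log-rank claim just as well as a Mann–Whitney one. It does not: such a claim is only not excluded.

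A reader might also infer that this trial's false-positive rate is 7.1%, or that its log-rank will exceed 5%. The documents do not support that either. They never say that the log-rank p-value comes from chi-square, and the software's defaults are outside them. The excess is also not steady: it vanishes with four to six participants at the limit, is large with seven, and changes with ties. Nor is it peculiar to the log-rank, since an uncorrected normal-approximation Mann–Whitney also exceeds 5%.

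Finally, the excess is about 2 points in the usual case, in a 10-person pilot that enrols no patients, and part of the disagreement reflects Mann–Whitney's conservatism. That limits the weight of the point. It does not remove it: the Protocol states that the goal is evidence for deploying the app in Geneva and elsewhere, and at this sample size the choice of test can settle the conclusion.

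**Conclusion.** The point holds as an omission with a measurable consequence. Two tests at 5% bear on one primary outcome with no deciding test and no p-value method, so a claim that complies with the plan can carry more than the stated 5%. The size is conditional: 7.1% for a chi-square log-rank, or for a claim on either test, with none to three at the limit, and 5.6% for an uncorrected normal-approximation Mann–Whitney without ties. Exact Mann–Whitney keeps to 5% throughout. These figures rest on 5 v 5, on distinct times below the limit, and on large-sample references that the SAP neither states nor excludes.

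The power shortfall does not depend on which p-value is reported for the log-rank. The planned Mann–Whitney, taken as exact, has about 68% power at d = 2 under normal data, not 80%. The matter should be corrected, but it is modest and does not call the design into question.

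**What to change.** Before the data are unsealed, amend the SAP as follows:

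- Name one test that decides the primary outcome at two-sided 5%, with an exact p-value that allows for ties. Exact Mann–Whitney is simplest because it is already planned. A permutation log-rank is equally valid if its statistic is named in advance.
- Label the other test and the Kaplan–Meier curves supportive.
- Keep anyone not done by 120 minutes in the analysis, at the tied worst rank for Mann–Whitney and censored for the log-rank, and say that such a participant is not missing under the complete-case rule.
- Apply the same rule to the secondary outcome.
- Restate power for the deciding test: for exact Mann–Whitney, about 68% at d = 2, reaching 80% only at about d = 2.3.

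The cost is a few sentences and a check that the named software gives an exact Mann–Whitney p-value with ties; a permutation log-rank may need other software. The downside is that the stated power becomes less favourable: about 68% for exact Mann–Whitney, or 73% to 75% for the permutation log-rank.
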